### 11.1. Multiplicity

The protocol specifies that a gatekeeping closed testing procedure will be used to control the family-wise Type I error rate at the 2-sided significance level of 0.05 for the primary and secondary efficacy endpoints. Due to the early termination of the study, however, no multiplicity adjustment will be performed.

### 11.2. Missing Data Handling

#### 11.2.2. Binary Efficacy Endpoints

##### 11.2.2.1. Primary Approach for Analysis

For binary efficacy endpoints, the primary approach to handling missing data will be nonresponder imputation (NRI), where subjects who are included in the denominator at the time point under consideration but have insufficient data for response determination at that time point will be considered nonresponders for that time point.

To eliminate the downward bias to the estimate of a binary endpoint due to the inclusion of subjects (as nonresponders due to NRI) who have not had a chance to reach the time point under consideration but have discontinued due to “study terminated by sponsor”, the denominator at

the time point under consideration will include subjects who have either completed that time point

or discontinued at any time due to reasons other than “study terminated by sponsor”, instead of all subjects in the ITT population.

[Redacted]

[Redacted]

[Redacted]

[Redacted]

[Redacted]

The within-group proportion, standard error (SE), and 2-sided 95% CI [REDACTED] for the within-group proportion will be provided for placebo, GED-0301 treatment regimens, and GED 160 (combining all 3 GED-0301 treatment regimens). The treatment comparison will be made between GED 160 and placebo. The unstratified treatment difference in proportions, stratified treatment difference in proportions using the weighted average of the treatment differences across the strata with the Cochran-Mantel-Haenszel (CMH) weights, stratified 2-sided 95% CI [REDACTED] for the treatment difference in proportions, and the 2-sided p-value from the CMH test stratified by the randomization stratification factors, will be provided for the comparison of GED 160 and placebo.

[REDACTED]

[REDACTED]

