## 3.2. End of Study

The End of Study is defined as either the date of the last visit of the last subject to complete the post-treatment follow-up or the date of receipt of the last data point from the last subject that is required for primary, secondary and/or exploratory analysis, as prespecified in the protocol, whichever is the later date.

Study completion for an individual subject is defined as reaching the Week 52 Visit. Subjects not meeting this definition will be considered early termination subjects. Subjects who discontinue from the study at Week 12 (either because they meet the early escape criteria or for any other reason) will complete the Week 12 Visit. Subjects who prematurely discontinue from the study at any other time prior to the Week 52 Visit, including subjects who early escape into the Long-term Active-treatment Study, will complete the Early Termination (ET) Visit (Section 6.3). The ET Visit should be scheduled as soon as possible after the last dose of IP.

Subjects who complete the Week 52 Visit, as well as subjects who prematurely discontinue from the study and do not enter into the Long-term Active-treatment Study, will have a 4-week Follow-up Visit. If the ET Visit occurs 28 days or more after the last dose of IP, then the Follow-

up Visit is not required. Subjects entering the Long-term Extension Study will not have the Follow-up Visit.

CELGENE PROPRIETARY INFORMATION

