### 11.1. Treatment Discontinuation

The following events are considered sufficient reasons for discontinuing a subject from the investigational product(s):

- Lack of efficacy
- Adverse Event
- Withdrawal by subject
- Death
- Lost to follow-up
- Other (to be specified in the eCRF)
- Pregnancy

The reason for discontinuation of treatment should be recorded in the eCRF and in the source documents.

The decision to discontinue a subject from treatment remains the responsibility of the treating physician, which will not be delayed or refused by the Sponsor. However, prior to discontinuing a subject, the Investigator may contact the Medical Monitor and forward appropriate supporting documents for review and discussion.

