Subjects may discontinue the study at any time. Subjects who discontinue from the study at Week 12 (either because they meet the early escape criteria or for any other reason), will complete the Week 12 Visit. Subjects who prematurely discontinue from the study at any other

[figure not shown]
time prior to the Week 52 Visit, including subjects who early escape into the Long-term Active-treatment Study, will complete the Early Termination (ET) Visit. The ET Visit should be scheduled as soon as possible after the last dose of IP.

Subjects who complete the Week 52 Visit, as well as subjects who prematurely discontinue from the study, will have a 4-week Follow-up Visit. If the ET Visit occurs 28 days or more after the last dose of IP, then the Follow-up Visit is not required.

Subjects entering the Long-term Extension Study will not have the Follow-up Visit.

A schematic of the study design is in [Figure 1](#).

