### 5.3. Analysis Populations

#### 5.3.1. Intent-to-treat Population

The intent-to-treat (ITT) population will be the primary population for the efficacy analysis. The ITT population is defined to include all subjects who are randomized and receive at least 1 dose of IP.

Due to the early termination of the study, for binary efficacy endpoints, the denominator at the time point under consideration will include subjects who have either completed that time point

or discontinued at any time due to reasons other than “study terminated by sponsor”, instead of all subjects included in the ITT population (Section 11.2.2.1).

Subjects will be included in the treatment group to which they were randomized for the efficacy analysis using the ITT population.

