## 11. EFFICACY ANALYSIS

All efficacy analysis tables will be presented by GED-0301 treatment regimen, placebo, and a total group combining all 3 GED-0301 treatment regimens. The 3 GED-0301 treatment regimens will be labeled as GED 160/GED 160 4 WK ALT, GED 160/GED 40 4 WK ALT, and GED 160/GED 40, and the total group combining all 3 GED-0301 treatment regimens will be labeled as GED Total. Formal treatment comparisons will be made between GED Total (ie, GED 160) and placebo for the efficacy analyses of the first 12 weeks, and between each of the 3 GED-0301 treatment regimens and placebo for the efficacy analyses beyond Week 12.

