## 11.4. Analyses of Secondary Efficacy Endpoints

### 11.4.1. Primary Analyses of Secondary Efficacy Endpoints

The primary analysis of each secondary efficacy endpoint will be performed similarly to the primary analysis of the primary endpoint. The treatment comparisons will be made between GED 160 (combining all 3 GED-0301 treatment regimens) and placebo for the endpoints at Weeks 4 and 12 and between each of the 3 GED-0301 treatment regimens and placebo for the endpoints at Week 52.

The analysis of the proportion of subjects who achieve corticosteroid-free clinical remission at Week 52 among subjects receiving oral corticosteroids at baseline will be based on the subjects included in the ITT population who receive oral corticosteroids for CD at baseline.

[REDACTED]

[REDACTED]

[REDACTED]

[REDACTED]

[REDACTED]

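### On the visible text, subjects enrolled too late to reach Week 52 can enter the Week 52 denominator only as nonresponders, which pulls within-arm Week 52 rates down

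*SAP*

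**What the plan says.** SAP 2 reports that the sponsor stopped the study after an October 2017 recommendation of the Data Monitoring Committee. SAP 5.3.1 then replaces the full ITT denominator for binary endpoints: "the denominator at the time point under consideration will include subjects who have either completed that time point" and, as a second route, those who "or discontinued at any time due to reasons other than" sponsor termination. SAP 11.2.2.1 and 16 repeat the rule. Anyone in the denominator without enough data at the time point is a nonresponder (NRI).

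The stated purpose in SAP 11.2.2.1 is to remove the downward bias from subjects "who have not had a chance to reach the time point under consideration but have discontinued due to" sponsor termination.

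The rule reaches the long-term endpoints. SAP 11.4.1 says: "The primary analysis of each secondary efficacy endpoint will be performed similarly to the primary analysis of the primary endpoint". SAP 11 plans formal comparisons "between each of the 3 GED-0301 treatment regimens and placebo for the efficacy analyses beyond Week 12". Five of the seven visible secondary efficacy endpoints need Week 52: remission, ER-50, corticosteroid-free remission, sustained remission and endoscopic remission.

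**The concern.** The first route requires the subject to have reached the time point. The second has no visible condition on enrolment date. For a subject enrolled less than 52 weeks before the stop, inclusion at Week 52 therefore depends on having already left. Those still on study disappear from the analysis; those who left stay in as failures.

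Exits for non-sponsor reasons are part of the design. "Lack of efficacy" is a listed reason for discontinuing treatment in Protocol 11.1, and for leaving the study in 11.2. Early escape is open from Week 12, and SAP 4.1 handles it as early termination: "including subjects who early escape into the Long-term Active-treatment Study, will complete the Early Termination (ET) Visit". Protocol 3.2 defines completion as reaching Week 52 and adds: "Subjects not meeting this definition will be considered early termination subjects".

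What is at stake is the accuracy of the reported Week 52 rates and of the regimen-versus-placebo differences built from them.

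**Working it through.** **The plan's own figures.** With a pooled-variance two-group chi-square test at two-sided 0.05, the power values in SAP Table 5 reproduce:

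- remission at Week 12 (266 vs 798, 22% vs 36%): 99.3%, stated 99%;
- remission at Week 52 (266 vs 266, 22% vs 36%): 94.7%, stated 95%;
- ER-50 at Week 52 (266 vs 266, 10% vs 20%): 90.0%, stated 90%.

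The SAP gives no figure for the residual bias.

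**Direction, without assumptions.** Let R be Week 52 responders, C completers, De non-sponsor dropouts among subjects with 52 weeks of opportunity, and Dl non-sponsor dropouts among later enrollees. The visible rule gives R/(C + De + Dl). The opportunity cohort gives R/(C + De). The first is lower whenever R and Dl are both above zero. For example, 36/100 = 36% becomes 36/120 = 30% with 20 late dropouts.

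**Size.** Let g be the share with 52 weeks of opportunity and q the share of the rest who left earlier for other reasons. The reported rate is the opportunity-cohort rate times

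f = g / (g + (1 − g)q).

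Neither g nor q is in the documents. To show a range, assume a constant dropout hazard with proportion d lost by Week 52, and potential follow-up of late enrollees uniform over 0 to 52 weeks. Then q = 1 − d/(−ln(1 − d)), which is 0.104, 0.217 and 0.345 for d = 20%, 40% and 60%.

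| f | g = 0.25 | g = 0.5 | g = 0.75 | g = 0.9 |
|---|---|---|---|---|
| d = 20% | 0.763 | 0.906 | 0.967 | 0.989 |
| d = 40% | 0.606 | 0.822 | 0.933 | 0.976 |
| d = 60% | 0.491 | 0.743 | 0.897 | 0.963 |

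**Worked case, g = 0.5 and d = 40% in both arms.** f = 0.5/(0.5 + 0.5 × 0.217) = 0.822. Placebo 22% × 0.822 = 18.1%; active 36% × 0.822 = 29.6%; the difference is 11.5 points instead of 14. For ER-50, 10% and 20% become 8.2% and 16.4%. A simulation of 2 million subjects at a true 36% gave 29.6% under the visible rule and 36.0% in the opportunity cohort, with no late enrollee counted as a responder.

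Without the SAP's rule, NRI on all ITT subjects would give 11% and 18% here (g times the true rate). The rule thus repairs most of the damage but not all.

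**Unequal dropout, g = 0.5.** f is 0.863 at 30% dropout and 0.782 at 50%. With 30% active and 50% placebo, the difference is 36 × 0.863 − 22 × 0.782 = 13.9 points. With 50% active and 30% placebo, it is 36 × 0.782 − 22 × 0.863 = 9.2 points.

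**Week 12.** Only subjects enrolled within 12 weeks of the stop are affected. With 80% to 95% having 12 weeks of opportunity and 5% to 20% dropout by Week 12, the same formula gives f = 0.975 to 0.999.

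**The case against.** **The rule does what the SAP says it does.** A reader might infer that the SAP fails its own aim of eliminating the bias. The text does not support that. The aim covers subjects discontinued because the sponsor stopped the study, and the rule removes exactly those. The residual bias is a different component, which the SAP does not claim to address.

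**Retained dropouts are true failures under NRI.** Protocol 9.6.1 counts subjects with insufficient data as nonresponders, and a late enrollee who left for lack of efficacy fits that. This stands as far as it goes. The difficulty is that comparable late enrollees still on study are removed, so only the failures of that group remain. The documents do not name the opportunity-cohort rate as the target. However, if early and late enrollees are exchangeable, it is also the rate for the whole ITT population. At g = 0.5 and 40% dropout, the reported rate lies below the all-ITT rate unless late enrollees' true rate is at most f(1 − q) = 0.822 × 0.783 = 0.64 times the early rate.

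**Redaction.** In SAP 16 text is blacked out directly after the completer route, and several blocks in 11.2.2.1 are redacted. The abbreviation list defines DAO and MNAR, which the visible analysis text does not use. A qualifier or a sensitivity analysis may exist. The second route itself reads as complete, so the point holds on the visible text and needs the sponsor's confirmation.

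**Inflated Type I error.** A reader might infer that the rule manufactures false positives. With equal dropout it does not: the null rejection rate stays at about 5%. With 30% versus 50% dropout at g = 0.5 and 266 per arm, simulation gives 7.2%. That needs remission among completers of 22/0.70 = 31% in one arm and 22/0.50 = 44% in the other, so that better completers exactly offset heavier dropout. The documents show neither the unequal dropout nor the offset.

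**Magnitude rests on assumptions.** This is correct. A constant hazard also fits poorly with an escape route that opens only at Week 12, and the error could go either way.

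**Conclusion.** The concern holds for Week 52 rates on the visible text. The downward direction is algebraic and needs only one late enrollee who left for a non-sponsor reason and at least one Week 52 responder in that arm. The size is unknown: under the stated assumptions f runs from 0.49 (g = 0.25, 60% dropout) to 0.99 (g = 0.9, 20% dropout). With equal dropout the treatment difference shrinks by the same factor; with dropout that differs by arm, which is possible but not shown, it can move either way.

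The consequence is limited. SAP 11.1 drops multiplicity adjustment, and Protocol 9.6.2 treats unadjusted p-values as a measure of strength of association. What remains affected is the set of reported long-term estimates and comparisons. It should be fixed, with medium confidence because of the redactions.

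**What to change.** First, have the sponsor confirm whether the redacted text in SAP 11.2.2.1 and 16 already sets an opportunity condition or an equivalent sensitivity analysis. If the condition exists, only the *at any time* wording needs aligning with it.

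Otherwise, in SAP 5.3.1, 11.2.2.1 and 16, define the Week-t denominator as all ITT subjects whose Week-t visit window (first dose plus t weeks plus the 3 days allowed in Protocol Table 3) closed on or before the date sites were told to stop dosing, site by site if those dates differ. Include them whatever their time or reason of leaving, and apply NRI within that set. Report the current rule as a sensitivity analysis; it also keeps any Week-t data observed just outside the cutoff.

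**Cost.** A date filter and SAP wording; no new data.

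- Week 52 denominators shrink. At g = 0.5 and 40% dropout, if 266 per arm were enrolled, 266 × (0.5 + 0.5 × 0.217) = 162 becomes 266 × 0.5 = 133.
- Under equal dropout nominal power does not fall: 68% to 71% for remission and 61% to 63% for ER-50. It can fall if placebo loses more subjects (84% to 71% at 30% active and 50% placebo dropout).
- Failures observed in late enrollees leave the main analysis, and results represent earlier enrollees, for whom eligibility criteria differed by amendment.
- The cutoff must be accurate. Set 4 weeks too late at g = 0.5, the factor is 0.5/(0.5 + 0.5 × 4/52) = 0.929, which turns 22% and 36% into 20.4% and 33.4%.

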## 11.4. Analyses of Secondary Efficacy Endpoints

### 11.4.1. Primary Analyses of Secondary Efficacy Endpoints

The primary analysis of each secondary efficacy endpoint will be performed similarly to the primary analysis of the primary endpoint. The treatment comparisons will be made between GED 160 (combining all 3 GED-0301 treatment regimens) and placebo for the endpoints at Weeks 4 and 12 and between each of the 3 GED-0301 treatment regimens and placebo for the endpoints at Week 52.

The analysis of the proportion of subjects who achieve corticosteroid-free clinical remission at Week 52 among subjects receiving oral corticosteroids at baseline will be based on the subjects included in the ITT population who receive oral corticosteroids for CD at baseline.

[REDACTED]

[REDACTED]

[REDACTED]

[REDACTED]

[REDACTED]

**11.7. Assessing Study Center Effect and Treatment-by-center Interaction**

This study is a multicenter study and has hundreds of study sites planned. The limited number of subjects expected at many sites does not allow for a meaningful assessment of study center effect.

## 12. SAFETY ANALYSIS

Safety will be evaluated via descriptive statistics and point estimates. No inferential testing for statistical significance will be performed.

The safety analyses will be based on the safety population. All safety analysis tables will be presented by GED-0301 treatment regimen, placebo, and a total group combining all 3 GED-0301 treatment regimens. The 3 GED-0301 treatment regimens will be labeled as GED 160/GED 160 4 WK ALT, GED 160/GED 40 4 WK ALT, and GED 160/GED 40, and the total group combining all 3 GED-0301 treatment regimens will be labeled as GED Total.

The table content is redacted with a large grey block. A diagonal watermark 'CELGENE PROPRIETARY INFORMATION' is overlaid across the redacted area.

## 12.2. Adverse Events

Adverse events will be coded according to the MedDRA. Unless otherwise specified, AEs will be summarized by SOC and PT, with SOCs sorted in alphabetical order and PTs within each SOC in descending order of subject incidence of the total group combining all 3 GED-0301 treatment regimens.

For the analyses of AEs, the following point estimates are provided, unless otherwise specified:

- Subject incidence: Subject incidence (ie, percentage [%] used in a frequency summary) is defined as the number of subjects with the specific event divided by the number of subjects included in the analysis. Subjects with multiple occurrences of the specific event in the specific analysis period will be counted only once in the numerator.

- 

All AE summaries will be provided for Weeks 0-52. Where so indicated, select AE summaries will also be provided for Weeks 0-12 and/or Weeks 12-52.

A subject data listing of all AEs (including treatment-emergent AEs [TEAEs] and non-TEAEs) will be provided.

### 12.2.1. Overall Summary of TEAEs

An overall summary of the following TEAE categories will be provided for Weeks 0-12, Weeks 12-52, and Weeks 0-52:

- Any TEAE
- Any drug-related TEAE
- Any severe TEAE
- Any serious TEAE

- Any serious drug-related TEAE
- Any TEAE leading to drug interruption
- Any TEAE leading to drug withdrawal
- Any TEAE leading to death

#### **12.2.2. All TEAEs**

All TEAEs will be summarized by SOC and PT as well as by PT only (in descending order of subject incidence of the total group combining all 3 GED-0301 treatment regimens) for Weeks 0-12, Weeks 12-52, and Weeks 0-52.

#### **12.2.3. Drug-related TEAEs**

Drug-related TEAEs will be summarized for Weeks 0-12, Weeks 12-52, and Weeks 0-52.

#### **12.2.4. TEAEs by Maximum Severity**

All TEAEs will be summarized by maximum severity (mild, moderate, and severe) for Weeks 0-52. If a subject reports multiple occurrences of a specific event within a specific analysis period, the subject will be counted only once by the maximum severity. If the severity is missing for one or more of the occurrences, the maximum severity of the remaining occurrences will be used.

#### **12.2.5. Serious TEAEs**

Serious TEAEs will be summarized for Weeks 0-12, Weeks 12-52, and Weeks 0-52.

A subject data listing of all serious AEs (both TEAEs and non-TEAEs) will be provided.

#### **12.2.6. TEAEs Leading to Drug Withdrawal**

TEAEs leading to drug withdrawal will be summarized for Weeks 0-12, Weeks 12-52, and Weeks 0-52.

A subject data listing of AEs leading to drug withdrawal will be provided.

#### **12.2.7. Deaths**

A subject data listing of all deaths will be provided.

### **12.3. Clinical Laboratory Evaluations**

The following protocol-specified parameters from the central laboratory will be summarized:

- Hematology panel will include: complete blood count (CBC) with differential, including red blood cell (RBC) count, hemoglobin, hematocrit, mean corpuscular hemoglobin (MCH), mean corpuscular hemoglobin concentration (MCHC), mean corpuscular volume (MCV), white blood cell (WBC) count (with differential), and platelet count.
- Serum chemistry panel will include: total protein, albumin, calcium, phosphorous, glucose, total cholesterol, triglycerides, uric acid, total bilirubin, alkaline phosphatase, aspartate aminotransferase (AST)/serum glutamic oxaloacetic transaminase (SGOT),

alanine aminotransferase/serum glutamic pyruvic transaminase (SGPT), sodium, potassium, chloride, carbon dioxide, blood urea nitrogen (BUN), creatinine, lactic dehydrogenase (LDH), magnesium.

- Complement activation (Bb, C3a and C5a).
- Coagulation assessment will include: prothrombin time and activated partial thromboplastin time (APTT).
- Urinalysis will include specific gravity and pH,.

Summary statistics of observed values and changes from baseline will be provided by time point (time points include the scheduled visits for labs, the follow-up visit, the end of Weeks 0-12, the end of Weeks 12-52, and the end of Weeks 0-52).

Frequency summaries (shift tables) of shifts from baseline to post-baseline time points (time points include the scheduled visits for labs, the end of Weeks 0-12, the end of Weeks 12-52, the end of Weeks 0-52, and the worst value of Weeks 0-52) by category of low/normal/high/both low and high (the last category for the shift to the worst value only) will be provided for hematology and serum chemistry.

A summary of laboratory marked abnormalities as defined in Section 18.4 will be provided for Weeks 0-52.

A separate summary of laboratory marked abnormalities will also be presented by normal baseline and abnormal baseline.

A subject data listing of all laboratory data (including urinalysis) will be provided.

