### 6.5.3. Clinical Laboratory Assessments

Clinical laboratory evaluations will be performed by a central laboratory to include the following laboratory assessments performed at the frequency specified in [Table 3](#):

- Hematology panel will include: complete blood count (CBC) with differential, including red blood cell (RBC) count, hemoglobin, hematocrit, mean corpuscular hemoglobin (MCH), mean corpuscular hemoglobin concentration (MCHC), mean corpuscular volume (MCV), white blood cell (WBC) count (with differential), and platelet count.
- Serum chemistry panel will include: total protein, albumin, calcium, phosphorous, glucose, total cholesterol, triglycerides, uric acid, total bilirubin, alkaline phosphatase, aspartate aminotransferase (AST)/serum glutamic oxaloacetic transaminase (SGOT), alanine aminotransferase (ALT)/serum glutamic pyruvic transaminase (SGPT), sodium, potassium, chloride, carbon dioxide, blood urea nitrogen (BUN), creatinine, lactic dehydrogenase (LDH), magnesium, and complement activation (Bb, C3a and C5a).
- Coagulation assessment will include: prothrombin time (PT) and activated partial thromboplastin time (APTT)
- Urinalysis will be done at the central lab and will include specific gravity, pH, glucose, ketones, protein, blood, bilirubin, leukocyte esterase, nitrite, and urobilinogen. Microscopic urinalysis (bacteria, casts, crystals, epithelial cells, RBC, and WBC) will be performed only if the dipstick urinalysis is abnormal.

Clinical laboratory evaluations are not required to be fasting. However, the site will record whether a clinical laboratory evaluation was fasting or nonfasting on the lab requisition form.

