### 9.7. Safety Analysis

Safety and tolerability will be assessed by clinical review of all relevant parameters including treatment-emergent adverse events (TEAEs), laboratory tests, vital signs, weight, and ECGs. No inferential testing for statistical significance will be performed.

TEAEs will be classified using the MedDRA classification system. All TEAEs will be summarized by system organ class, preferred term, severity, and relationship to IP. TEAEs leading to death or to discontinuation from treatment and serious TEAEs will also be tabulated. In the by-subject analysis, a subject having the same event more than once will be counted only once and by greatest severity.

Laboratory, vital signs, weight, and ECG data will be summarized descriptively by time point. In addition, shift tables showing the number of subjects with values low, normal, and high compared to the normal ranges at baseline versus postbaseline will be provided for laboratory tests.

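### In the visible text, SAP 12.3 summarizes only specific gravity and pH from urinalysis, leaving eight collected dipstick tests without the by-time-point summary that protocol 9.7 promises

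*SAP*

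**What the plan says.** **Collected.** Protocol 6.5.3 defines the urine panel: "Urinalysis will be done at the central lab and will include specific gravity, pH, glucose, ketones, protein, blood, bilirubin, leukocyte esterase, nitrite, and urobilinogen". A reflex step follows: "Microscopic urinalysis (bacteria, casts, crystals, epithelial cells, RBC, and WBC) will be performed only if the dipstick urinalysis is abnormal". Protocol Table 3 schedules urinalysis at screening, baseline, Weeks 12, 20, 28, 36, 44 and 52, early termination and follow-up.

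**Promised.** Protocol 9.7 states: "Laboratory, vital signs, weight, and ECG data will be summarized descriptively by time point". It then adds that low/normal/high shift tables for "baseline versus postbaseline will be provided for laboratory tests". Neither statement leaves out urinalysis.

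**Planned.** SAP 12.3 opens its list with "The following protocol-specified parameters from the central laboratory will be summarized". The hematology, chemistry, complement and coagulation entries carry over the protocol's panels. The urinalysis entry is "Urinalysis will include specific gravity and pH", followed by a stray comma and full stop. By-time-point statistics apply to the listed parameters, and shift tables are confined to hematology and serum chemistry. A marked-abnormality summary for Weeks 0-52 is also planned, with a second version split by normal or abnormal baseline, but the criteria in Section 18.4 are not in the public text. Finally: "A subject data listing of all laboratory data (including urinalysis) will be provided".

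**The concern.** The SAP's rule is narrower than the protocol's. The protocol commits to summarizing laboratory data over time, whereas the SAP names two of ten urine tests and gives the panel no shift table. Clinically significant change in laboratory findings is a secondary safety endpoint (protocol Table 2, SAP Table 3). The two retained tests do not show new urine protein, blood or glucose, and a subject listing is not a comparison between groups. A modest difference between GED-0301 and placebo in dipstick results could therefore go unnoticed if few of those results were reported as adverse events.

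**Working it through.** The plan gives no figure to reproduce here. The check compares the lists.

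**Step 1: count the tests.** Protocol 6.5.3 names "specific gravity, pH, glucose, ketones, protein, blood, bilirubin, leukocyte esterase, nitrite, and urobilinogen", which is 10 tests. SAP 12.3 names 2. The difference is 10 − 2 = 8: glucose, ketones, protein, blood, bilirubin, leukocyte esterase, nitrite and urobilinogen. The 6 reflex microscopy items (bacteria, casts, crystals, epithelial cells, RBC, WBC) are not in the SAP's list either.

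**Step 2: set the SAP 12.3 outputs side by side.**

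| Panel | By-time-point summary | Shift table | Subject listing |
|---|---|---|---|
| Hematology | yes | yes | yes |
| Serum chemistry | yes | yes | yes |
| Complement (its own entry in the SAP) | yes | not named | yes |
| Coagulation | yes | not named | yes |
| Specific gravity, pH | yes | not named | yes |
| Other 8 dipstick tests | not named | not named | yes |

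The last row is the only part of the routine panel that gets neither kind of summary. Whether the marked-abnormality summary reaches any of these tests cannot be determined.

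**Step 3: look for a declared change.** The visible bullets of SAP Section 16 cover the efficacy denominator and the dropped multiplicity adjustment. None mentions urinalysis. Other bullets there are blacked out.

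**Step 4: look for another route to a by-arm table.** Protocol 6.5.5 has clinically significant abnormal laboratory findings after the first dose recorded as adverse events. Protocol 10.3 treats a laboratory abnormality as an adverse event if it leads to discontinuation, needs treatment or another intervention, or is judged clinically important. SAP 12 and 12.2.2 tabulate TEAEs by regimen, placebo and GED Total for Weeks 0-12, 12-52 and 0-52. Significant urine findings therefore do reach a by-arm table. Dipstick changes that are not reported as adverse events do not, unless Section 18.4 picks them up.

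**The case against.** - **Clinically significant changes are already covered.** The endpoint concerns clinically significant laboratory changes, and Step 4 shows that these pass into the TEAE tables. This stands and limits the point. A reader might infer that a urine imbalance would appear in no table, or that these tests survive only in listings. The documents support neither, because the adverse-event route exists and the marked-abnormality criteria cannot be read. What remains is that the adverse-event route depends on investigator reporting, and that a marked-abnormality summary for Weeks 0-52 would not be a summary by time point.
- **The choice has a plain reason.** Specific gravity and pH are numeric. The other tests usually come back as graded or positive/negative results (general laboratory practice; the documents do not give the result format), so means and low/normal/high categories fit them poorly. This argues against means, not against a frequency or shift table. SAP 12.5 already plans a categorical shift table for ECG interpretation.
- **Other tests give partial cover.** Serum creatinine, BUN, albumin, total protein, bilirubin and glucose keep both by-time-point summaries and shift tables. That is true, but blood tests do not stand in for urine protein or blood.
- **Text may be missing after pH.** The stray comma leaves this possible. However, the word before pH closes a two-item list, and the protocol prints the same test names unredacted, so an editing remnant is more likely.
- **The change may be declared in Section 16.** With bullets redacted there, an undeclared departure cannot be asserted. A declaration would settle the documentation but would not supply the summary.

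**Conclusion.** The point holds and is minor. In the visible text, eight of the ten dipstick tests have no by-time-point laboratory summary and no shift table, although protocol 9.7 promises both without excepting urinalysis. The loss is a systematic between-group view of dipstick changes not reported as adverse events. Only descriptive safety reporting is affected: efficacy inference, power and Type I error are untouched.

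This rests on two readings: that the SAP's urinalysis entry is complete at two items, and that no blacked-out safety text adds a by-time-point urine summary. The documents report no urinary signal, and the study stopped early, so they give no basis for putting a size on any imbalance that might be missed.

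**What to change.** In SAP 12.3, add a categorical shift table (normal/abnormal, or graded where the laboratory reports grades) for glucose, ketones, protein, blood, bilirubin, leukocyte esterase, nitrite and urobilinogen. Show the shift from baseline to each scheduled urinalysis visit and to the worst post-baseline value in Weeks 0-52, by regimen, placebo and GED Total. Correct the stray punctuation in the urinalysis entry at the same time. If the sponsor prefers to keep the shorter list, Section 16 should state the reduction and the reason for it, unless a redacted bullet already does so.

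The cost is a few extra tables from central-laboratory data that are already collected. No new assessments are needed.
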